5.3 Storage

All interventional devices are owned, stored, and managed by the Center for Neuromodulation in Depression and Stress (CNDS). All devices are stored behind locked doors with restricted access to members of the CNDS. These devices are located at the CNDS lab-space in the Richards Biomedical Building.

5.4 Blinding

The administering clinician will be blinded as a part of this study. All subjects will receive TMS to both stimulation sites (fMRI-guided target/ DLPFC) as a part of this study in 2-week intervals. The order of site of stimulation is randomized and counterbalanced.

5.5 Administration and Accountability

Staff will be trained on the protocol and inclusion/exclusion criteria. TMS protocols will be administered by specially-trained staff in the CNDS. All TMS staff will be trained by the PI ([name].) and the Center Director ([name].). These procedures are in accordance with the "Safety, ethical considerations, and application guidelines for the use of transcranial magnetic stimulation in clinical practice and research" (Rossi et al., 2009). MRI scans will be conducted by MRI technologists trained at the Center for Advanced Magnetic Resonance Imaging and Spectroscopy (CAMRIS).

6 Study Procedures

Procedure Visit Number	Screening (2-3 Hours)	Baseline (2- 3 Hours)	TMS Treatment (1 ½ hours)	*3 week break* 2 Phone calls (30-60 minutes) N/A	TMS Treatment (1 ¹ / ₂ hours)	Follow-Up Calls (30-60 minutes) N/A
Visit Type	In-person (Virtually during COVID-19)	In-person	In-person	Phone	In-person	Phone/ Surveys
Study Duration	2-3h	2-3h	1-2h	30min	1-2h	30min
Informed Consent	Х					
Clinical Assessments	Х	Х	X	Х	X	Х
Neurocognitive Assessments		Х	X (Visit 11 Only)		X (Visit 22 Only)	
MRI		Х				
TMS	X (Demonstration Only)		X		X	
Behavioral Tasks			Х		Х	
EEG and eyetracking		Х	X (Visit 11 Only)		X (Visit 22 Only)	

***Visit 11 and Visit 22 may take up to 2 hours to complete

During the COVID-19 pandemic the screening visit and other procedures may be completeled remotely.

Does your study use MRI? (CAMRIS is the appropriate contact for all studies involving MRIs) \boxtimes Yes \square No

Check of all that apply: □ 1.5T MRI

	1.51	MR
\boxtimes	3T N	1RI
	7TM	RI

Does the MRI use investigational sequences and/or coils? (See Experimental Device Clause)

🗌 No

⊠ Yes

Unsure (if unsure you need to contact CAMRIS)

Does your study include pregnant women? (See Pregnancy Clause and Justification)

Yes

Does the MRI require the use of Contrast Agents? (See Contrast Risks)

CONFIDENTIAL

This material is the property of the University of Pennsylvania.

🛛 No

	□ Yes	No	
Does your stud	y involve the exposure to	radiation, radiotracers and/or radiological imaging modalities?	
	Yes	\boxtimes No (If No, no RRSC review is needed)	
Will any of the i of a subject's pa	radiation exposure result articipation in the researc Yes	from procedures that are or could be performed solely as a result the protocol? \fbox No	
Ultrasound	□ Yes	⊠ No	
Will your study	be using CT Scans? (CA □ Yes	CTIS is the appropriate contact for studies involving CT scans) \fbox No	
Check off all of the following procedures that will be performed in your research- each option you select will link to the template language document:			
	Leukapheresis		
	Bone Marrow Biopsy	/ or Aspirate	
	Use of AP clinical sp	ecimens	
	Biopsies- check thos	e which apply	

Blood draw

6.1 Screening

Prior to any study visits, all subjects will be screened in a telephone interview with a trained member of the study staff or complete a self-report screening survey.

Those who pass the screen will receive an appointment to come to the research location to review the informed consent form and conduct the baseline diagnostic assessment screen to determine eligibility. Informed consent will be obtained upon arrival at this initial visit and before any study-related procedures are conducted. All subjects will have the opportunity to ask questions before signing a consent form. The rest of this initial visit will be an extended screening, which includes a structured diagnostic interview, psychiatric and medical evaluation, and collection of demographic information. Subjects will undergo a short demonstration of TMS to ensure that they are comfortable with all study procedures. This process involves adjusting the TMS device to a moderate level of stimulation and administering single pulses to the prospective TMS sites. A structured interview, Diagnostic and Statistical Manual of Mental Disorders - DSM-5 will be used to assess the DSM criteria for PTSD or trauma induced MDD and the PHQ-9 will be used to assess presence of depressive symptoms. If subjects have time limitations, we may provide the option to complete the some of these assessments remotely (by phone/ sending the surveys) or to split the visit in two visits. Additionally, during the COVID-19 pandemic, the screening visit will be conducted virtually. If any of these adjustments are made, we will make a note in their records. For participants that indicated regular drug use in prescreening or screening forms, we may use a urine drug screen to confirm adherence to study policy of abstinence. The urine drug screen will be collected by study staff; test results will be stored in REDCap and the test destroyed immediately after.

6.2 Study Intervention Phase

6.2.1 Visit 1 (sometimes referred to as the baseline visit)

Visit 1 (aka Baseline) will take approximately 2-3 hours. If participants have time limitations, we may provide the option to complete the clinical assessments remotely (by phone/ sending the surveys) or to split the visit in two visits. If any of these adjustments are made, we will make a note in their records. At the first study session, subjects will complete 60 minutes of structural MRI and resting-state fMRI scans. Structural and functional scans will be obtained in each session on a clinically-approved 3 Tesla Siemens Prisma (Erlangen, Germany) scanner, equipped with 40mT/m gradients and 200 mT/m/s slew-rates. RF transmission will use a quadrature body-coil, and reception will use a Siemens receive-only 64-channel head coil. The total time in the scanner will be approximately 60 minutes. An experienced technician and a member of the study team will be present during the MR session to ensure participant safety and well-being.

Additionally, clinical assessments of thoughts, mood, and behaviors will be completed. Subjects will complete the following neurocognitive assessments during this visit:

- i. Nback task: Computerized task to measure working memory capacity.
- ii. Trails A & B task: Computerized task of visual attention and task switching.
- iii. Stroop/Word task: Neurophysiological testing of cognitive interference.
- iv. Foraging task: Computerized test to measure reward seeking behaviors.

In collaboration with [name] from the [name] Lab, EEG data will be collected when the participants are engaged in the above-mentioned tasks. We may also record the location of their gaze at any particular time during these tasks using a passive eye-tracking device. The eyetracker will use a camera to identify the position of the pupil and cornea (using near-infrared reflection). By tracking the gaze of the subjects as they make decisions, we can obtain information about what subjects attended to during their decisions, for how long they attended to it, and in what order they attended to it.

6.2.2 Visits 2 - 11

Visits 2-11 are the first set of TMS treatment visits; each visit will take approximately 1 ½ to complete. If participants have time limitations, or during the COVID-19 pandemic, we may provide the option to complete the clinical assessments remotely (by phone/ sending the surveys) and we will make a note in their records. Brain data from the MRI scan (stimulation target in individualized brain space) will be calibrated with the skin and scalp using a Polaris Vicra camera (Brainsight neuronavigation) to allow marking of the stimulation sites. In addition, subjects will be evaluated to determine their motor threshold, or the amount of stimulation at the motor cortex needed to create an involuntary thumb twitch. This preparation time is expected to take approximately 30 minutes. Then, the TMS devices will be used to administer theta-burst stimulation (. TBS will be administered twice per session, with approximately a 20 minute break between each round of TMS. Participants will complete a short clinical assessment before and after each TBS session.

During the break between TMS rounds, participants will either complete a working memory task or watch a peaceful video;. These tasks are being added to the study protocol in order to activate brain areas through which the TMS treatments are expected to enhance relaxed mood (nature videos) or increase cognitive control (nback working memory task). Randomization will be by random number generator with eventual matching by demographics (age, race, gender) to balance the groups later in the study, as necessary.

During TMS, subjects will be asked to sit still for approximately seven minutes at a time when TBS is administered. The total number of stimulations in each TBS block is 1200 stimulations, for a total of 2400 stimulations. We approximate that the additional single pulses to determine motor threshold will not exceed 100 additional pulses. At the end of each TBS session, participants will complete additional clinical assessments. If participants have time limitations, we may provide the option to complete the clinical assessments remotely (by phone/ sending the surveys), and we will make a note in their records. TBS sessions are expected to take approximately 1 ½ hours, except for Visit #11 and visit #23 which will involve CONFIDENTIAL

additional clinical and neurocognitive assessments and will last approximately 2 hours During these neurocognitive assessments, we may collect EEG and eyetracking data, as in the Baseline Visit.

We may use Neuroflow software for recording participants' heart rate during each TMS treatment session. NeuroFlow's software platform analyzes data from a commercially available, third-heart rate monitor. NeuroFlow follows strict HIPAA guidelines with respect to patient privacy and data security, both from a technical and administrative respective. Only de-identified data will be recorded using this platform, no identifiers will be entered on the platform.

Participants will have a 3 week break from TMS treatment between the first set of TMS sessions (i.e., Visit 2-11/Weeks 1 & 2) and the second set of TBS sessions (i.e., Visits 13-23/Weeks 6 & 7). During this time, participants will not be coming into the lab. However, participants will be scheduled for two phone/survey visits approximately one week, and two weeks (+/- 3 days) following Visit #11, in which clinical assessments will be completed.

Due to the nature of TMS treatment, daily visits are necessary. In the event a participant misses a session, the participant may complete two TMS treatment sessions on one day with ample time in between. In this case, the principal investigator will consider the timeline of missed sessions and evaluate how the missed sessions may be made up appropriately. If too many sessions are missed (as per PI discretion), the participant may be withdrawn from the study without their consent.

6.2.3 3 week break & Phone Calls

Participants will have a 3 week break from TMS treatment between the first set of TBS sessions (i.e., Visit 2-11/Weeks 1 & 2) and the second set of TBS sessions (i.e., Visits 13-22/Weeks 6 & 7). During this time, participants will not be coming into the lab. However, participants will be scheduled for two phone calls and Check-In surveys approximately one week (+/- 3 days) and two weeks (+/- 3 days) following Visit #11, in which clinical assessments will be completed.

6.2.4 Visits 13 - 22

Visits 13-22 are the second set of TMS treatment visits and will consist of identical procedures and will take the same amount of time as Visits 2-11, but stimulations occurring at the targeted site not used in the initial round of TMS treatments Please see sections 6.2.2 for further explanation on these visits.

6.2.5 6 Month Follow-Up: Phone Calls

Upon completion of the study, scheduled phone and survey visits will take place every 4 weeks (+/- 7 days) over the subsequent 6-month period to monitor continued stability of clinical improvement and/or remaining clinical symptoms. Each phone and survey visit will include clinical assessments and will take approximately 30-60 minutes.

6.3 Subject Withdrawal

Subjects may withdraw from the study at any time. They may also be discontinued from the study at the discretion of the Investigator for lack of adherence to intervention, study procedures, or visit schedule. The Investigator or the Sponsor (if applicable) may also withdraw subjects who violate the study plan or to protect the subject for reasons of safety or for administrative reasons. It will be documented whether or not each subject completes the study. No tapering procedure with TBS is necessary or required in the event that a subject withdraws from this study.

6.4 Pregnancy Testing

Consistent with clinical care standards for MRI scanning, attestation of pregnancy status will be accepted at the time of MRI screening. In addition, attestation of pregnancy status will be requested prior to TMS treatment.

6.5 Other Evaluations, Measures

During the course of the study, patients' symptoms will be evaluated in order to determine changes in symptoms across the study. Symptom scales are detailed below in the "Efficacy Evaluations" section.

6.6 *Efficacy Evaluations*

The following clinical assessments will be utilized at baseline, after the first 2-week period of TMS treatment, during the TMS treatment 3 week break, and after the second 2-week period of TMS treatment (the end of the study) to evaluate the efficacy of the TMS interventions in improving clinical symptoms:

- Patient Health Questionnaire (PHQ-9)
- PTSD Checklist for DSM-5 (PCL-5)
- Montgomery-Asberg Depression Scale (MADRS)
- Columbia Suicide Severity Rating Scale (CSSRS)
- Positive and Negative Affect Schedules (PANAS 20 item)
- World Health Organization Quality of Life (WHOQOL-BREF)
- Snaith-Hamilton Pleasure Scale (SHAPS)

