Study Duration	8 months (Screening, 9 weeks of treatment visits with a 3-week break, and 6 months of phone/survey follow-up visits)		
Study Center(s)Center for Neuromodulation in Depression and Stress University of Pennsylvania School of Medicine Department of Psychiatry			
Objectives	We aim to compare the efficacy of rTMS treatment to two sub-regions of the Dorsolateral Prefrontal Cortex (DLPFC). We will examine the standard positioning of TMS used in clinical settings compared with TMS using MRI to guide the precise location of stimulation. We hypothesize that fMRI-guided TMS will produce greater benefit to patients with MDD/PTSD than the standard targeting method for TMS.		
Number of Subjects	N=80; n=40		
Main Inclusion and Exclusion Criteria	18-60; inclusive; no TMS contraindications; no medication use that substantially reduces seizure threshold or interferes with fMRI recordings; PTSD diagnosis or trauma induced MDD (SCID interview) and elevated depression (PHQ \ge 10).		
Investigational Product (drug, biologic, device, etc.)	MagVenture devices for rTMS administration include: -MagPro X100* magnetic stimulator -Cool-B65 Butterfly Coil		
Duration of administration (if applicable)	2 sets of 10 consecutive weekdays (at minimum 4 sessions per week with a total of 10 overall sessions per set)		
Reference therapy	N/A		
Statistical Methodology	Clinical outcome will be evaluated on symptom scales in a TMS target x Time ANOVA. Similarly, rate of change (slope) x TMS Target will indicate how rapidly each treatment improves symptoms.		

Safety Evaluations	TMS protocols will be administered by specially-trained staff from the Center or Neuromodulation in Depression and Stress the University of Pennsylvania Department of Psychiatry. All TMS staff will be trained by the PI ([name].) and the Center Director ([name].).		
Data and Safety Monitoring Plan	The PI will be responsible for monitoring the data quality and the ongoing safety of subjects.		

CONFIDENTIAL

BACKGROUND AND STUDY RATIONALE

Introduction

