6.7 Safety Evaluations

Only individuals trained by the Principle Investigator ([name].) and Center Director ([name].) will dispense TMS. The licensed physician ([name] or a suitable medically trained stand-in) will closely supervise any medical instability in patients and will specifically be responsible for training and overseeing syncope and seizure management which are not expected given our screening process but are the two primary health risks with TMS treatment.

[name], a board certified physician, will review all questionable screens for MRI and TMS safety and will be physically present (or a reasonable medically trained stand-in) for every TMS session conducted on any participant who indicates greater than minimal risk for experiencing syncope or a seizure in response to TMS.

Only research personnel will have keys and access to the TMS devices.

7 Statistical Plan

All recruitment will be conducted through the University of Pennsylvania, the Veterans Administration Medical Center, and surrounding community to find 80 patients with PTSD or trauma induced MDD and depressive symptoms. It is anticipated that a large portion of individuals will screen fail, withdrawal from participation or have unusable data. Therefore, 80 individuals will be consented/enrolled in this study, to ensure that there are 40 patients who complete the full protocol with usable data. This sample should provide us with adequate data to compare treatment sites relative to one another, since all patients will receive the standard targeting for TMS and also fMRI-guided TMS.

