7.4.4 Safety Analysis

All subjects entered into the study will have detailed information collected on adverse events throughout the study duration, and this information will be used for the overall study safety analysis. These factors will include: worsening of symptoms, development of new psychiatric symptoms, medical effects (syncope, seizure, or other), and any equipment failures.

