8.5 Medical Monitoring

[name], a board certified physician, will review all questionable screens for MRI and TMS safety and will be physically present (or a reasonable medically trained stand-in) for every TMS session conducted on any participant who indicates greater than minimal risk for experiencing syncope or a seizure in response to TMS which are the primary medical risks for this procedure. It is the responsibility of the Principal Investigator to oversee the safety of the study in collaboration with [name] and other collaborating medical staff. This safety monitoring will include careful assessment and appropriate reporting of adverse events as noted above.

Participants will meet the clinician treating them at each TMS treatment visit where they also report on their current symptoms. During the 3 week break, we also call them to assess symptom changes. Substantial worsening of symptoms to the point of potential threat determined by the study physician ([name]) and Pl (licensed psychologist) will result in a threat assessment of the patient which, depending on the degree of worsening, will facilitate: brief de-escalation interventions, request for self-admit to nearest emergency room, request for family/friend accompaniment to ER, or a call to emergency services for patient pick up. The procedures are all done within walking distance of the Department of Emergency Medicine at Penn Medicine, which will be the first choice for emergency services if the patient is ambulatory and willing to accompany study staff to the hospital. The VA hospital is also within walking distance and will be the preferred ER for veteran participants.

If the patient endorses a significant worsening of symptoms that is abnormal for their typical illness course or puts them into a category of imminent risk for self-harm, their participation will be discontinued.

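### The C-SSRS is assigned only to efficacy (6.6), and the safety analysis (7.4.4) neither links its scores to adverse events nor tabulates suicidality by target and round

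*Combined protocol and SAP*

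**What the plan says.** Section 6.6 (Efficacy Evaluations) lists seven scales, the C-SSRS among them. They "will be utilized at baseline, after the first 2-week period of TMS treatment, during the TMS treatment 3 week break" and again after the second treatment period, and their stated purpose is "to evaluate the efficacy of the TMS interventions in improving clinical symptoms". Section 6.5 refers the reader to that list for the study's symptom scales. The Study Summary then says: "Clinical outcome will be evaluated on symptom scales in a TMS target x Time ANOVA".

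The safety sections do not mention the C-SSRS. Section 6.7 covers staff training, physician cover, device access and "overseeing syncope and seizure management which are not expected given our screening process but are the two primary health risks with TMS treatment". Section 7.4.4 works from adverse events: "All subjects entered into the study will have detailed information collected on adverse events throughout the study duration". It adds: "These factors will include: worsening of symptoms, development of new psychiatric symptoms, medical effects (syncope, seizure, or other), and any equipment failures". Section 8.1.1 makes adverse event status depend on the Principal Investigator finding that something has become significantly worse.

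Section 8.5 handles suicidality patient by patient. A participant whose worsening "puts them into a category of imminent risk for self-harm, their participation will be discontinued".

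**The concern.** The plan treats suicidality as a harm serious enough to end participation, yet the only purpose it states for its dedicated suicidality scale is to show benefit. A mean is a poor summary for this. A few patients who become clearly worse can be offset by many who improve slightly, and the mean then shows no change or a small improvement.

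Attribution is the second problem. Section 3.1 gives every patient both targets in randomized order, and comparing the two targets is the primary objective (2.1). An adverse event list that is not divided by target and round cannot show which target a suicidality signal followed. The participants are depressed, have PTSD or trauma-induced MDD, and are not taking psychiatric medication (4.1, 4.2), so this is a harm on which a reader will expect a clear count.

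**Working it through.** **Tracing the scale through the plan**

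1. The C-SSRS appears once, in 6.6. It is not named in 6.7, 7.4.4, 8.1 or 8.2.
2. Section 6.5 identifies the 6.6 list as the symptom scales, and the Summary sends symptom scales to a target-by-time ANOVA. The Summary's companion analysis of slopes also compares averages. Section 7.4 names only the Hamilton scale. Section 7.4.2 speaks of clinical symptoms without naming a scale or a method. The Summary's analysis is therefore the only one that reaches the C-SSRS.
3. The route into the safety analysis is 7.4.4, then the adverse event definition in 8.1.1, then the Principal Investigator's judgement. No C-SSRS score or change is tied to that judgement. Section 3.1.2 says the researchers know the stimulation site. Section 5.4 says the administering clinician is blinded, and the two need reconciling. There is no DSMB (8.5.2).
4. Patients discontinued under 8.5 may have no post-round score. Section 7.5 says only that completed time-points may be used, and section 7 sizes the trial on 40 patients who complete with usable data. An ANOVA of means can therefore lose the patients who worsened most.

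**What a mean can conceal**

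The plan has no figure of its own to reproduce here. The scores below are assumptions. The documents do not describe C-SSRS scoring, so a whole-number ideation score is assumed. The 40 is the planned number of evaluable patients (4.5).

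- Case A: 3 patients rise by 3, 12 fall by 1, 25 are unchanged.
  - Mean change = (3×3 − 12×1)/40 = −3/40 = −0.075.
  - SD = √[(3×9 + 12×1 − 40×0.075²)/39] = √(38.775/39) = 1.00.
  - t = −0.075/(1.00/√40) = −0.48.
  - Patients who worsened: 3/40 = 7.5%, exact (Clopper-Pearson) 95% CI 1.6% to 20.4%.
- Case B: 4 rise by 3, 15 fall by 1, 21 are unchanged.
  - Mean change = (12 − 15)/40 = −0.075.
  - SD = √(50.775/39) = 1.14, t = −0.42.
  - Patients who worsened: 4/40 = 10%, exact 95% CI 2.8% to 23.7%.

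The mean is the same in both cases and reads as no change. The count separates them. The result does not depend on the assumed scoring, because any mean nets rises against falls.

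**What a count can deliver at this size**

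- Chance of seeing at least one case in 40 = 1 − (1 − p)^40: 33%, 64%, 87% and 99% (0.985) for a true per-round incidence p of 1%, 2.5%, 5% and 10%.
- With no cases, the upper limit of the exact 95% interval is 1 − 0.025^(1/n). For n = 40 (one target, both rounds) it is 8.8%. For n = 20 (one target in one round, 40/2 if the two orders are equal) it is 16.8%.

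**The case against.** A reader might infer that new suicidal ideation or behaviour is averaged away instead of being counted as a harm, and that a signal would be missed. The documents do not support that.

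- Section 7.4.4 covers all subjects entered and expressly counts worsening and new psychiatric symptoms. New or worse ideation fits both.
- Serious suicidal behaviour can meet the serious adverse event criteria in 8.1.2.
- Section 3.1 uses the two break contacts as a safety assessment. Section 3.2.3 places an end-of-round clinical assessment under safety endpoints. Section 10.1 gives the safety monitor access to the symptom scales.
- Section 8.5 has symptoms reported at each TMS visit, a threat assessment for substantial worsening, and discontinuation for imminent self-harm risk.

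It can also be said that no passage names an analysis of the C-SSRS. Section 1.1, where it names measures for judging each site, gives the MADRS, PCL and WHOQOL only. That the scale goes into the ANOVA is a reading of 6.5, 6.6 and the Summary together, and the illustrative scores were chosen so that rises and falls nearly cancel.

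All of this stands, and it rules out the stronger claim. Two gaps remain. These provisions protect individual patients and allow events to be recorded, but none says how a C-SSRS result enters the safety analysis. None assigns a case to a target or round.

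**Conclusion.** The point holds as a gap in the safety analysis. It does not show that suicidality goes unmonitored or uncounted. The C-SSRS has one stated use, efficacy, and the only stated analysis that reaches it compares means. Suicidality enters the safety analysis only through investigator judgement, without reference to the scale and without division by target or round.

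The size cannot be derived from the documents. The illustration shows that 7.5% or 10% of 40 patients could worsen while the mean change stays at −0.075, but it rests on assumed scores and on the ANOVA being applied to the C-SSRS. The absence of any tabulation by target and round rests on neither assumption. The change should be made: it is cheap, and it concerns the comparison the trial is designed to make.

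**What to change.** Cross-list the C-SSRS in 6.7 and 7.4.4. It may also stay in 6.6. In 7.4.4, pre-specify the following:

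- **Count.** For each target and each round, among all participants who started that round, give the number and percentage with new or worsened suicidal ideation or any suicidal behaviour, with exact confidence intervals. State how many had no post-round score.
- **Reference score.** Use the last C-SSRS collected before that round's first stimulation. For round 2 this is the later of the two break contacts that has a score or, if neither has one, the score after round 1. Say whether break scores count towards round 1. Otherwise a rise first seen in the break becomes the round 2 reference and is counted nowhere.
- **Discontinuations.** List participants discontinued under the 8.5 self-harm rule by target and round, and count them even without a post-round score.

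Clinical thresholds and stopping rules stay with the investigators and do not change. The cost is one paragraph and one table from data already collected. The intervals will be wide at about 40 patients, so the table describes harm at each target and will not support a claim that the targets are equally safe.
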